1.3 Secondary Study Endpoints

The secondary endpoint is subjective ratings of the film and side effects in order to determine whether blood levels are of significant magnitude for the participant to detect drug effects.

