1.0 Objectives

1.1 Study Objectives

The objective of this study is to test the effect of a range of doses of a novel nicotine film on plasma nicotine levels and, via a questionnaire, subjective ratings of the film and side effects. We predict that delivery of nicotine via the film will produce plasma nicotine levels akin to other methods of nicotine replacement therapy (NRT) and that it will be easy to use, safe, and well tolerated. The nicotine film is not part of standard of care and is not available in a non-investigational setting in the United States.

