7.2 Study Procedures

Part 1- Screening (Phone)

Participants will be instructed to drink water prior to their visit to help the blood draw process go smoothly. They will also be instructed that they may choose to have a meal from our cafeteria but may also bring snacks if they would like. Participants will also be informed that they can bring personal items such as laptops, books, etc. for use during their visit.

Part 1-Screening (In Person)

Participants will be re-screened for eligibility and informed consent for the appropriate part of the study will be obtained by research staff.

After consent, additional eligibility screening materials will include:

1. A review of medications and medical history
2. NIDA Drug Screener
3. Blood Pressure (systolic must be \leq 140, diastolic must be \leq 90)
4. Urine pregnancy test (if applicable)
5. Exhaled Carbon Monoxide <12 ppm

Part 1 Visit – 4 Hours

Clinical measures and questionnaires will be conducted as outlined in the table below. An IV will be inserted for access for 11 blood draws in Part 1.

Part 1: Time and Events Table						
	Screening	Part 1 Procedures				
Visit Hour	-2	-1	0	1	2	3
Administer Film			X			
Blood Draws (mins)			0-59	60-119	120-179	180-239
Baseline Blood		X				
Hour 0 Blood			Set Minutes: 5, 10, 20, 30, 40, 50 Varied by Participant: 1 minute after film dissolves			
Hour 1 Blood				Minute 60		
Hour 2 Blood					Minute 120	
Hour 3 Blood						Minute 180
Measures						
Screener 2	X					
Concomitant Meds	X					
Medical History	X					
NIDA	X					
CES-D		X				
Oropharyngeal Exam		X				X
Blood Pressure & Heart Rate	X	X	Minute 30	Minute 0, 30	Minute 0, 30	Minute 0, 30
CO Reading	X					X
Pregnancy Test	X					
Anthropometrics		X				
Demographics		X				
Nicotine Dependence		X				
Cigarette Details		X				
Tobacco Use History		X				
Minnesota Withdrawal Scale		X	Minute 15, 35, 55	Minute 20	Minute 20	Minute 20
Questionnaire of Smoking Urges		X	Minute 15, 35, 55	Minute 20	Minute 20	Minute 20
Study Product Side Effects			Minute 15, 35, 55	Minute 20	Minute 20	Minute 20
Study Product Evaluation						X
Likelihood of Use Scale						X
Payment						\$120

Film Administration, Dose and Blood Draws:

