Hour 6 Blood									Set Mins: 0,30,45					
Hour 7 Blood										Min 0				
Hour 8 Blood											Min 0			
Hour 9 Blood												Set Mins: 0, 30,45		
Hour 10 Blood													Min 0	
Hour 11 Blood														Min 0
Study Hour	-2	-1	0	1	2	3	4	5	6	7	8	9	10	11
Measures														
Screener 2	X													
Concomitant Medications	X													
Medical History	X													
NIDA	X													
CES-D	X													
Oropharyngeal Exam		X												X
Blood Pressure & Heart Rate	X	X	Min 30	Min 0, 30	Min 0, 30	Min 0, 30	Min 0, 30	Min 0, 30	Min 0, 30	Min 0, 30	Min 0, 30	Min 0, 30	Min 0, 30	Min 0
CO Reading	X													
Pregnancy Test	X													
Anthropometrics	X													
Demographics	X													
Dependence	X													
Cigarette Details	X													
Tobacco Use History		X												
Minnesota Withdrawal Scale		X	Min 50	Min 50		Min 50	Min 50		Min 50	Min 50		Min 50		Min 50

Questionnaire of Smoking Urges		X	Min 50	Min 50		Min 50	Min 50		Min 50	Min 50		Min 50	Min 50
Study Product Side Effects			Min 50	Min 50		Min 50	Min 50		Min 50	Min 50		Min 50	Min 50
Study Product Evaluation						Min 0							X
Likelihood of Use Scale						Min 0							X
Dose Awareness													X
Payment													\$240

Film Administration, Dosing and Blood draws:

Participants will receive four doses of nicotine film during this visit. Four participants each will be randomly allocated to consume four films over twelve hours in the following orders (a) 0,0,0,0mg (b) 2,2,2,2, or (c) 4,4,0,4. The first film will be administered upon completion of baseline measures (approximately 8AM). Again, participants will be instructed to allow the film to dissolve in their mouth, without chewing or swallowing it and to report to the researcher when he or she feels that the film has completely dissolved. Films will be administered every three hours (approximately 11 AM, 2 PM, and 5 PM). The Time and Events table above details the order of events and timing for biomeasures, questionnaires and 20 total blood draws.

Payment:

Participants will receive \$240 for completing this visit.

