7.4.2 Treatment Regimen

Nicotine films will be administered orally. They are used by placing a film on the tongue, closing the mouth and pressing the tongue gently to the roof of the mouth. The film will dissolve in the mouth within 5-10 minutes. Three doses of nicotine film will be used in this study: 0, 2, and 4 mg. During the first part, participants will receive one dose of either 0, 2, or 4 mg film. After the first part is complete, reactions to dosing will be evaluated and adjustments will be made if necessary before proceeding to the second part. Should adjustments need to be made, modified protocol and consent documents will be submitted to the IRB prior to proceeding to Part 2. During the second part, participants will receive four doses of nicotine film at three hour intervals over the course of twelve hours. There will be three dosing groups and four participants each will receive all 0 mg films, all 2 mg films, or a sequence of 4,4,0,4 mg films.

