9.2 Statistical methods

Paired sample t-test (or nonparametric Wilcoxon Rank-Sum test) will be used to examine the changes in the outcome measures (plasma nicotine, subjective measures, HR, BP) from the baseline.

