11.7 Statistical tests

Statistical methods will be used to analyze the safety data to determine whether harms are occurring. Paired sample t-test (or nonparametric Wilcoxon Rank-Sum test) will be used to examine the changes in the outcome measures (plasma nicotine, subjective measures, HR, BP) from the baseline.

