- **Nicotine film side effects:** Excess nicotine can cause mild symptoms such as nausea, dizziness, diarrhea and rapid heartbeat. Occasionally these symptoms are more severe (e.g. vomiting) such as when an individual receives more nicotine than they are accustomed to. This, however, is unlikely to occur with the doses used in this study. Additional side effects of the film may include hiccups.

- **Possible effects on the oral cavity.** In order to assess local toxicity of the study product, the CRC nurse assisting with the clinic visit will perform an oropharyngeal exam at the beginning of the visit prior to the participant receiving the study product as well as at the end of the visit after study product use is complete. Any changes will be assessed and documented. During the visit, after each film administration, participants will be asked to report side effects including any mouth discomfort or irritation via a questionnaire. If indicated, participant would discontinue study product use. Lesions of the oral mucosa are not anticipated as daily dissolution of several 2 mg sublingual nicotine tables (range 1-12/day over a 6 month period) led to only mild and transient effects on the oral mucosa[24]
- **Incidental Finding:** None of the tests carried out in this study are intended to provide diagnoses for clinical purposes, but participants will be alerted to findings that should be discussed with a healthcare provider (such as high blood pressure)

The participant may be removed from the research study without his or her permission because the participant does not follow the instructions for the study, has an adverse reaction to the study product (irregular heartbeat, palpitations, tachycardia (resting heart rate persistently greater than 100 beats per minute), has symptoms of nicotine overdose such as nausea, vomiting, dizziness, weakness, or rapid heartbeat, or has symptoms of an allergic reaction.

Participants are instructed to please call the Principal Investigator, [name] [name]., at [contact] during business hours or [contact] after business hours if they:

- Experience any symptoms after the study is completed that they believe may be related to participation in the study
- Have questions, complaints, or concerns about the research

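### The film-rating and side-effect scales in the secondary endpoint have no pre-film score for the planned change-from-baseline test, and no outcome is compared with 0 mg

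*Combined protocol and SAP*

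**What the plan says.** Section 1.3 states: "The secondary endpoint is subjective ratings of the film and side effects in order to determine whether blood levels are of significant magnitude" for participants to notice the drug. Section 1.1 gives the overall aim: "The objective of this study is to test the effect of a range of doses of a novel nicotine film on plasma nicotine levels". The design in section 7.1 is randomised, blinded and parallel-group. Section 7.2 puts four participants on each of 0, 2 and 4 mg in Part 1. For Part 2, section 7.4.2 says "four participants each will receive all 0 mg films, all 2 mg films, or a sequence of 4,4,0,4 mg films".

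Section 9.2 is one sentence. It names a paired t-test, or a Wilcoxon rank-sum test as the nonparametric alternative, which "will be used to examine the changes in the outcome measures (plasma nicotine, subjective measures, HR, BP) from the baseline". Section 11.7 repeats this for safety: "Paired sample t-test (or nonparametric Wilcoxon Rank-Sum test) will be used to examine the changes in the outcome measures". No section describes a comparison between dose groups.

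On timing, section 12.0 says that "after each film administration, participants will be asked to report side effects including any mouth discomfort or irritation via a questionnaire". The Time and Events tables in section 7.2 give the schedule for each scale. Sections 11.2 and 11.6 list data for review, including all Part 1 data before Part 2 opens, but name no reference group.

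**The concern.** A paired test of change needs a baseline score for each participant. The scales that rate the film and its side effects appear to have none, so the stated method does not fit the stated secondary endpoint. If subjective measures in 9.2 means only the withdrawal and smoking-urge scales, which do have a baseline, then film ratings and side effects have no stated analysis.

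The second gap is the unused control. A third of participants in each part receive 0 mg under blinding, yet no outcome is contrasted with them. Asking whether people can detect a drug effect means telling it apart from the taste of the film, expectation and the passing of time since the last cigarette. A change within active arms cannot do that.

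With several scales and many time points, leaving the analysis open means it could be chosen after the data are seen. The section 11.7 test for harms also has no defined use for the side-effect questionnaire.

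**Working it through.** **1. The plan's own figure.** Section 9.1 gives n = 12. Three groups of 4 make 3 × 4 = 12, which agrees. No alpha, SD, effect size or numerical power is given, so there is no power figure to reproduce. Section 9.2 does not say whether paired tests are run within each arm (n = 4) or over all 12.

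**2. Which scales have a baseline?** Counts from the two Time and Events tables in section 7.2:

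| Scale | Part 1 before film | Part 1 after | Part 2 before first film | Part 2 after |
|---|---|---|---|---|
| "Study Product Side Effects" | 0 | 6 | 0 | 8 |
| Product evaluation | 0 | 1 | 0 | 2 |
| Likelihood of use | 0 | 1 | 0 | 2 |
| Withdrawal scale | 1 | 6 | 1 | 8 |
| Smoking urges | 1 | 6 | 1 | 8 |

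In Part 1, side effects are asked at minutes 15, 35 and 55 of hour 0 and at minute 20 of hours 1, 2 and 3. In Part 2 they are asked at minute 50, starting in hour 0. Product evaluation and likelihood of use come in hour 3 of Part 1, and at hour 3 minute 0 and the end of the visit in Part 2. The Part 2 table is slightly broken in extraction, so the column of the last side-effect entry is unclear. The empty pre-film cells do not depend on that: both tables agree, the withdrawal and urge rows do carry an hour −1 mark, and section 12.0 places the side-effect questionnaire after each film.

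A recorded difference from a pre-film score therefore exists for 0 of 12 completers per part on each of the first three scales. Plasma nicotine, heart rate and blood pressure all have a pre-film value.

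**3. What a paired test does without 0 mg.** Illustration, assuming two-sided alpha 0.05 and normal changes: suppose all arms drift by 1 SD of the within-person change, with no drug effect. The noncentrality is 1 × √n. The chance of p < 0.05 is 29% at n = 4 and 88% at n = 12. Pooling all 12 lowers the change detectable with 80% power from 2.13 SD to 0.89 SD, but mixes 0 mg with active doses.

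**4. What a 0 mg contrast can deliver (4 v 4, same assumptions, equal SDs).**
- 95% CI half-width: t(0.975, 6) × √(1/4 + 1/4) = 2.447 × 0.707 = 1.73 SD.
- Power from the noncentral t, 6 df, noncentrality d/√(1/4 + 1/4): 22% at d = 1, 66% at d = 2 and 80% at d = 2.38. With alpha halved for two contrasts, 80% needs d = 2.79.
- Exact rank-sum, no ties: smallest p = 2/C(8,4) = 2/70 = 0.029; next 4/70 = 0.057.
- Ties make it coarser: for 0,0,0,0 v 0,1,2,3, p = 2 × C(5,4)/70 = 10/70 = 0.143.
- Exact signed-rank within one arm of 4: smallest p = 2/2⁴ = 0.125.

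**5. The test name.** Rank-sum compares two independent samples; the counterpart of a paired t-test is signed-rank. The sentence names no groups, so the rank-sum wording cannot be read as a planned 0 mg comparison.

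**The case against.** **A zero baseline.** Before any film is used, its side effects could be taken as zero, and change then equals the post-film score. This is a reasonable reading, and it stands to this extent: a reader might infer that the whole secondary endpoint is incomputable, and for side effects the documents support only that the baseline is undefined. They do not state the zero. The reading gives no help for product evaluation or likelihood of use, since a film not yet tried has no rating.

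**Plasma nicotine.** A reader might infer that the missing 0 mg contrast undermines the primary endpoint equally. It does not. Taste and expectation do not raise plasma nicotine, dosing is watched on site (section 7.4.4), a pre-film draw exists, and the prediction in section 1.1 is similarity to other nicotine replacement. What 0 mg adds is the decline of residual nicotine.

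**Withdrawal on placebo.** Section 12.0 says only that more serious withdrawal may occur on placebo. That is a risk disclosure, and it should not be read as a forecast of a difference.

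**Safety oversight.** Adverse events, subjective effects and the full Part 1 data are reviewed whatever section 11.7 says (sections 11.2, 11.5 and 11.6). The gap is in the stated test; the documents do not show that safety review would fail.

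**Size.** With 4 per arm the output is largely descriptive with or without a change. That is true, and it argues for estimates with intervals. It does not argue for leaving the contrast unnamed.

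**Conclusion.** The point holds and should be fixed. The stated test cannot be computed for product evaluation and likelihood of use, and has an undefined baseline for side effects. No outcome is compared with 0 mg. For subjective measures, heart rate and blood pressure, change from baseline alone cannot be credited to nicotine. For plasma nicotine it remains interpretable, and the gap is narrow. The nonparametric test is misnamed in both sections.

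A reader might also infer that the analysis will be picked after unblinding. The documents only leave it open, so this is a risk and not an established fact.

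The missing baselines rest on the schedule alone. The precision and power figures rest on an assumed two-sided alpha of 0.05, normal scores and equal SDs, and the rank-sum values of 0.029 and 0.057 on no ties.

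**What to change.** Change the wording of sections 9.2 and 11.7 before unblinding. Analyse each part separately, since section 16.0 lets a person join both.

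1. For film ratings and side effects, compare post-film scores of each active group with 0 mg, using one summary per participant fixed in advance: for example the maximum post-film side-effect score, and the end-of-visit product evaluation and likelihood-of-use scores. This needs no baseline. Report differences with 95% CIs as estimates, without formal significance claims across the two contrasts.
2. For plasma nicotine, heart rate, blood pressure, withdrawal and urges, keep change from baseline and add the difference in change between each active group and 0 mg.
3. Name signed-rank for paired changes and rank-sum for group comparisons.
4. State the low precision, and that a non-significant result does not show the drug to be undetectable or well tolerated.

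Optional and descriptive in Part 2: a single-film comparison from scores before the second film, the within-person contrast in the 4,4,0,4 arm, and the "Dose Awareness" item by regimen.

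The cost is a little more analysis work and wide intervals on the page. No new visits, blood draws, instruments or participants are needed.

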1.2 Primary Study Endpoints

The primary endpoint is plasma nicotine.

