9.0 Statistical Plan

9.1 Sample size determination

Initial testing by [name] (a principal investigator on the project and co-inventor of the oral nicotine film) has demonstrated that the plasma nicotine levels produced by oral nicotine film are comparable in size to those produced by consumption of a similar dose of Nicorette gum. Pharmacokinetic studies have shown that Nicorette gum has robust effects on plasma nicotine concentration that are readily detectable in sample sizes that are approximately the same as (e.g., Benowitz, Jacob, & Savanapridi, 1987; Lunell & Lunell, 2005), or smaller than (e.g., Shiffman et al., 2009), the one proposed here (n=12). Based upon such work, we are confident that we will have sufficient power to achieve the aim of the proposed research.

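### The secondary question is whether participants can feel the nicotine levels reached, but the plan only tests each outcome against its own baseline, with no comparison with 0 mg and no analysis relating ratings to nicotine

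*Combined protocol and SAP*

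**What the plan says.** All references are to the combined protocol and SAP.

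- **Primary endpoint (1.2):** "The primary endpoint is plasma nicotine". No summary measure is named.
- **Secondary endpoint (1.3):** ratings of the film and of side effects, collected "in order to determine whether blood levels are of significant magnitude for the participant to detect drug effects".
- **Analysis (9.2):** a paired t-test, or a rank-sum test as the nonparametric option, "will be used to examine the changes in the outcome measures (plasma nicotine, subjective measures, HR, BP) from the baseline". Section 11.7 repeats this for safety, introduced by "Statistical methods will be used to analyze the safety data to determine whether harms are occurring". Neither section names an arm, a time point or a comparison group.
- **Design (7.1, 7.2):** each part randomises 12 people, 4 per group. Part 1 gives one film of 0, 2 or 4 mg. Part 2 gives four films three hours apart, "in the following orders (a) 0,0,0,0mg (b) 2,2,2,2, or (c) 4,4,0,4". Nicotine and ratings are both collected serially, and Part 2 ends with a Dose Awareness item.

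No correlation, regression, dose trend or active-versus-placebo comparison appears anywhere in the plan.

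**The concern.** Section 1.3 asks about the relation between a blood level and an effect. Answering it needs a contrast in exposure, either between people given nicotine and people given none, or within a person as the level changes. The planned tests use neither. They ask whether nicotine rose and whether ratings moved, each on its own.

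Participants stay on site for the whole visit (7.4.4), and section 12.0 expects withdrawal symptoms, possibly worse on placebo. Urges and withdrawal may therefore shift with time, abstinence or expectancy in every arm. A significant change in an active arm could be read as the drug being felt when it was not. The reverse error is also possible: if nicotine holds withdrawal steady while it climbs on 0 mg, the active arm shows no change from baseline and a real effect is missed.

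**Working it through.** **1. The plan's own figure.** Section 9.1 supports 12 per part by analogy with gum studies and says "we are confident that we will have sufficient power to achieve the aim of the proposed research". It gives no alpha, power, effect size or SD, so the figure cannot be reproduced. Two-sided 0.05 is assumed throughout.

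**2. Which forms can take a change-from-baseline test** (Time and Events tables, 7.2).

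| Form | Pre-dose entry | Planned test possible |
|---|---|---|
| Withdrawal scale, smoking urges | yes | yes |
| Study Product Side Effects | none in either part | no |
| Study Product Evaluation | none, post-dose only | no |
| Dose Awareness (Part 2) | none, once at the end | no |

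The two forms closest to the wording of 1.3 are ones the test cannot use.

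**3. Two positive baseline tests say little about a link.** Take n=12 and a true change of 1.0 SD in both nicotine and rating. Both paired t-tests are significant in 78% of simulated trials when the two changes are unrelated within people, and in 83% when they correlate at 0.8.

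**4. Drift.** The simulation is of Part 1 with 4 people per dose. Ratings are taken at baseline and at 15, 35, 55, 80, 140 and 200 min, with unit variance, equal correlation of 0.5–0.7 between times, linear drift to 200 min in every arm, and no effect of nicotine. The planned test is read as any of six uncorrected paired t-tests in the 4 mg arm. All these values are assumptions.

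| Drift by 200 min | Planned tests, at least one significant | 4 mg v 0 mg, mean change |
|---|---|---|
| 0 | 23–25% | about 5% |
| 1 SD | 48–61% | about 5% |
| 1.5 SD | 68–85% | about 5% |

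The first row is multiplicity: a single planned test with no drift gives 5%. The rise down the column is drift, which cancels in the comparison with 0 mg. If the tests are instead pooled over all 12 and every arm's rating rises 1.0 SD from expectancy (assumed nicotine rises of 0, 2 and 4 SD by arm), both baseline tests are positive in 87% of trials.

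**5. The rating-on-level model.** Assume a one-compartment curve with half-life 2 h and between-person log-SD 0.4. With person and time effects and equal correlation between times, the slope test is falsely positive in about 5% of trials. If correlation instead decays with time (0.5 to 0.9 per 30 min), the same model is falsely positive in 16–25%. The 4 mg versus 0 mg comparison stays near 5% under both structures. Power for a slope of 0.15 SD per ng/ml, with equal correlation, is about 33–48% if the mean peak is 2 ng/ml per mg, and 12–16% at 1 ng/ml per mg. Section 2.3 reports a rise of less than 2 ng/ml from a 1 mg film, so the lower range is relevant. These figures should be read to within a few points.

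**6. Pairing ratings with draws.**
- In Part 1, the forms at 15, 35 and 55 min lie 5 min from a draw on each side (10/20, 30/40, 50/60), so a nearest-draw rule ties. The forms at 80, 140 and 200 min follow draws by 20 min.
- In Part 2, after films 1–3, the 50-min form follows the 45-min draw by 5 min. The 110-min form is 50 min after the 60-min draw but 10 min before the 120-min draw.

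**7. Carry-over in the 4,4,0,4 arm.** Let f = 0.5^(3/half-life in hours). In units of one film, levels at a fixed time after films 2, 3 and 4 are 1+f, f+f² and 1+f²+f³. The contrast is (2+f+f²+f³)/2 − (f+f²):
- 1 h: f = 0.125, so 1.071 − 0.141 = 0.93
- 2 h: f = 0.354, so 1.261 − 0.479 = 0.78
- 4 h: f = 0.595, so 1.579 − 0.948 = 0.63

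**The case against.** The strongest reply is that a rating change in an active arm already shows the level was felt. This fails because 0 mg ratings are never set against active ones, so time, expectancy and abstinence remain as explanations.

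Several other points stand in part.

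- Section 1.1 frames the study as dose effects on nicotine and ratings. With 4 per arm, any link analysis is exploratory. This limits the claim but does not supply the missing comparison.
- Section 9.2 does not say any-of-six or per-arm, so the percentages in step 4 belong to one reading. They also apply only to urges and withdrawal. The missing contrast holds on every reading.
- A rating-on-level regression is not safe by default. With a person effect alone it can produce a false link (step 5). Most of the protection against drift comes from the comparison with 0 mg.

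A reader might go further in three ways that the documents do not support. One is that the data cannot link level to effect: they can, since the 0 mg arm, the serial measurements and the 4,4,0,4 sequence are all there and only the analysis is absent. Another is that the trial has a false-positive rate of up to 85%: that figure depends on an assumed 1.5 SD drift and uncorrected testing. The third is that the Part 2 forms at Hour 10 Min 50 were left out. Only the withdrawal row appears to end at Hour 11 Min 50. Rows after the page break have one column fewer in the text available, so column positions there are unreliable.

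**Conclusion.** The concern holds for the plan as written and should be corrected. The stated secondary question is not answered by the only analysis specified, and for side effects and product evaluation that analysis cannot be carried out.

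For urges and withdrawal the possible error is large: about 48–61% against about 5% at 1 SD of drift. This rests on the assumed drift, equal correlation of 0.5–0.7 and the any-of-six reading, and 23–25% arises from multiplicity without any drift. That a baseline change cannot be attributed to nicotine does not depend on those values.

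**What to change.** Rewrite 9.2, and align 11.7, along these lines.

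1. **Secondary analysis:** compare each active arm with 0 mg, reporting the difference and its 95% CI. Use change from baseline, averaged over the post-dose forms, for urges and withdrawal. Use post-dose scores for side effects and product evaluation.
2. **Exploratory analysis:** for each scale, fit a repeated-measures model of rating on plasma nicotine that includes the 0 mg participants, with form time as a factor, a person effect and a within-person correlation that decays with time, or another method robust to serial correlation in so small a sample. Define the paired level as the preceding draw or an interpolated value. Interpolation suits the Part 2 110-min form better. Report the slope with its 95% CI.
3. **Support:** in Part 2, contrast film 3 with the mean of films 2 and 4 in the 4,4,0,4 arm, against the same contrast in the other arms. State that carry-over shrinks it to about 63–93% of one film's effect (assumed half-life 4 h to 1 h).

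Check the original Part 2 table before changing any form times, and add Hour 10 forms only if it confirms that they are missing.

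The cost is a paragraph of text and no new data. The drawback is low power. A 4 versus 4 t-test has 80% power only for a difference of about 2.4 SD (noncentral t, 6 df, noncentrality d × √(4/2)), and the slope model is weak (step 5). The results should be labelled descriptive, and a null result should not be read as no detectable effect.
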